7.7.3 Pharmacokinetics (PK) and Exposure/Response (PK/PD)

PK data will be tabulated by treatment group. In addition, dose proportionality, achievement of steady-state, and accumulation ratio based on C_{trough} concentrations, comparison of C_{trough} levels with corresponding values in study 20060349, and correlation of C_{trough} concentrations with biomarkers of disease activity will be evaluated. PK analyses will be further described in the PK analysis plan. PK/PD association will mainly be assessed graphically.

AMG 714 concentrations in serum will be summarized. Summary statistics for concentrations will be calculated and the results tabulated by time point for AMG 714 treatment groups. Levels of AMG 714 in serum will also be listed and both the individual and mean results plotted by time point.

For PK/PD assessments, individual patients' exposure measures obtained from the PK analysis will be graphically assessed with select PD endpoints and if associations are observed will be further elucidated with modelling and/or summaries by quartiles of exposure.

The following PD variables may be explored:

- Primary endpoint (VH:CD);
- Select secondary endpoints (IELs density);
- Select PROs (CeD-PRO);
- Select biomarkers of disease activity (e.g., Serum IL-15).

Change from baseline to Week 12 for these variables will be plotted against individual predictions of steady-state exposure. For subjects with missing values at Week 12, earlier post-dose values will be used (if available), but those data points will be marked on the plots.

7.7.4 Celiac Disease Patient Reported Outcome (CeD PRO)

The CeD PRO questionnaire was developed to assess symptom severity in clinical trials in subjects with celiac disease. Items in the questionnaire were formulated based on one-on-one interviews with patients with celiac disease, thus they reflect the symptoms that patients consider part of their celiac disease experience. The questionnaire is designed as a self-

administered daily diary, to be completed at the same time each day, and requires less than 10 minutes to complete. It includes nine items asking participants about the severity of celiac disease symptoms they may experience each day. Participants are asked to rate their symptom severity on an 11-point, 0 to 10 scale; from “not experiencing the symptom” to “the worst possible symptom experience”. Symptoms include abdominal cramping, abdominal pain, bloating, gas, diarrhoea, loose stool, nausea, headache and tiredness.

Subjects will be asked to maintain a daily e-diary for the CeD PRO instrument from baseline to final study visit.

The total CeD PRO score is calculated as the sum of scores of all nine questions in CeD PRO questionnaire. The smaller the total CeD PRO score, the milder the symptoms of the subject. For modelling purposes, the total CeD PRO score on weekly level is also calculated (the weekly total score is calculated as the mean of total daily scores of a given subject).

The CeD PRO will be analysed using a linear mixed effects repeated measures model (MMRM) with the baseline value, treatment group, site, sex, time point and a time point-by-treatment group interaction term as fixed effects with an underlying correlation structure between the time points that results in the best fit for the model. Subject will be included as a random effect.

Two separate models will be fitted: one for daily level data with time (days from baseline) as continuous variable and another for weekly level data with time (weeks from baseline) as a categorical variable.

For the daily level data, the following model will be fitted:

$$Y_{ijklm} = \mu + \alpha_j + \varphi_l + \tau_m + \beta \cdot \text{baseline CeD PRO}_{ij} + \gamma \cdot \text{day}_{ijklm} + \lambda_{jk} + \eta_i + \varepsilon_{ijklm}$$

where

Y_{ijklm} is the total CeD PRO score for subject i ($i = 1, \dots, n_j$) from treatment group j ($j = 1, 2, 3$), sex l ($l = 1, 2$) and site m ($m = 1, 2, 3$) at day k ($k = 0, 1, 2, \dots, 112$),

μ is the overall mean,

α_j is the fixed effect due to treatment j ,

φ_l is the fixed effect due to sex l ,

τ_m is the fixed effect due to site m , β is the parameter estimate of the baseline total CeD PRO score,

γ is the parameter estimate of day,

λ_{jk} is the fixed interaction effect due to treatment j and day k ,

η_i is the random effect due to subject i ,

ε_{ijklm} is the random error for subject i from treatment group j , sex l and site m for day k .

Note that the proper functional form of the time (day) will be explored, e.g. square of day might be added.

The following SAS program will be used for carrying out the daily level analysis:

```

proc glimmix data=cedpro_d;
  class subjid trt site sex;
  model cedpro_d = cedpro_d_bl trt site sex day trt*day / solution;
  random _residual_ / subject=subjid type=AR(1);
  estimate "150 mg AMG 714 vs Placebo" trt 1 0 -1 /alpha=0.05 cl;
  estimate "300 mg AMG 714 vs Placebo" trt 0 1 -1 /alpha=0.05 cl;
  lsmeans trt /alpha=0.05 cl;
  ods output CovParms=Cov_Par LSMeans=LS_est Estimates=Eff_est
        FitStatistics=Fit_Stat ParameterEstimates=Par_est
        Tests3=Type_3;
run;

```

For the weekly level data, the following model will be fitted:

$$Y_{ijklm} = \mu + \alpha_j + \gamma_k + \lambda_{jk} + \beta \cdot baseline\ CeD\ PRO_{ijklm} + \eta_i + \varepsilon_{ijklm},$$

where

Y_{ijklm} is the total CeD PRO score for subject i ($i = 1, \dots, n_j$) from treatment group j ($j = 1, 2, 3$), sex l ($l = 1, 2$) and site m ($m = 1, 2, 3$) at week k ($k = 0, 1, \dots, 16$),
 μ is the overall mean,
 α_j is the fixed effect due to treatment j ,
 φ_l is the fixed effect due to sex l ,
 τ_m is the fixed effect due to site m ,
 γ_k is the fixed effect due to week k ,
 λ_{jk} is the fixed interaction effect due to treatment j and week k ,
 β is the parameter estimate of the baseline total CeD PRO score,
 η_i is the random effect due to subject i ,
 ε_{ijklm} is the random error for subject i from treatment group j , sex l and site m for week k .

The following SAS program will be used for carrying out the weekly level analysis:

```

proc glimmix data=cedpro_w;
  class subjid trt site sex week(ref=FIRST);
  model cedpro_w = cedpro_w_bl trt site sex week trt*week / solution;
  random _residual_ / subject=subjid type=AR(1);
  estimate "150 mg AMG 714 vs Placebo" trt 1 0 -1 /alpha=0.05 cl;
  estimate "300 mg AMG 714 vs Placebo" trt 0 1 -1 /alpha=0.05 cl;
  estimate "Week 0: 150 mg AMG 714 vs Placebo" trt 1 0 -1
    trt*week 0 0 0 0 0 0 0 0 0 0 0 0 0 0 0 0 0 1
    0 0 0 0 0 0 0 0 0 0 0 0 0 0 0 0 0 0
    0 0 0 0 0 0 0 0 0 0 0 0 0 0 0 0 0 -1 /alpha=0.05 cl;
  estimate "Week 0: 300 mg AMG 714 vs Placebo" trt 0 1 -1
    trt*week 0 0 0 0 0 0 0 0 0 0 0 0 0 0 0 0 0 0
    0 0 0 0 0 0 0 0 0 0 0 0 0 0 0 0 0 1
    0 0 0 0 0 0 0 0 0 0 0 0 0 0 0 0 0 -1 /alpha=0.05 cl;
  estimate "Week 1: 150 mg AMG 714 vs Placebo" trt 1 0 -1
    trt*week 1 0 0 0 0 0 0 0 0 0 0 0 0 0 0 0 0 0
    0 0 0 0 0 0 0 0 0 0 0 0 0 0 0 0 0 0
    -1 0 0 0 0 0 0 0 0 0 0 0 0 0 0 0 0 0 /alpha=0.05 cl;

```

```
estimate "Week 16: 300 mg AMG 714 vs Placebo" trt 0 1 -1
        trt*week 0 0 0 0 0 0 0 0 0 0 0 0 0 0 0 0 0 0 0 0 0 0 0 0 0 0 0
        0 0 0 0 0 0 0 0 0 0 0 0 0 0 0 0 0 0 0 0 0 0 0 0 0 0 0 1 0
        0 0 0 0 0 0 0 0 0 0 0 0 0 0 0 0 0 0 0 0 0 0 0 0 0 0 0 -1 0 /alpha=0.05 cl;
lsmeans trt /alpha=0.05 cl;
lsmeans trt*week /alpha=0.05 cl;
ods output CovParms=Cov_Par LSMeans=LS_est Estimates=Eff_est
FitStatistics=Fit_Stat ParameterEstimates=Par_est
Tests3=Type_3;
run;
```

Due to the repeated structure of the data, the measurements within a subject will be correlated. Therefore, it is assumed that the overall covariance matrix of the response is block-diagonal (e.g. the observations between different subjects are not related, but the same correlation structure exists within subjects). In order to determine the covariance structure that best fits the data, the same model with different covariance structures is fitted. Initially, the models will be fitted assuming first-order autoregressive (AR(1)) variance-covariance structure. Common within and between treatment variance components (compound symmetry (CS), and Toeplitz covariance structures) will be further explored to increase sensitivity of statistical tests. The best model will be chosen by comparing the Akaike Information Criterion (AIC) of the models with different covariance structures.

Note that the value of `type` will be changed according to which covariance structure is being fitted.

The modelling results (parameter estimates, covariance parameter estimates, estimated treatment effect, marginal means estimates and results of the check of assumptions, e.g. the normality assumption) will be tabulated and 95% confidence intervals added, where appropriate. If the parametric assumptions are not met, then in addition to the above-specified model, a generalized estimating equation (GEE) approach will be used as well.

The baseline and post-baseline weekly total CeD PRO scores along with the change from baseline values will also be described by summary statistics and tabulated by treatment group. Change from baseline for the weekly CeD PRO scores of individual questions (calculated as the average score of a question within a week) will also be tabulated by week and treatment group and described by summary statistics. The scores of individual questions and the total daily CeD PRO scores will be listed, as well as the total and by question weekly CeD PRO scores. Individual and mean curves of both the total weekly and daily CeD PRO scores as well as the individual questions will also be plotted by time point and treatment group.

PP populations will be used for summarizing CeD PRO results.

7.7.5 Assessment of the gluten-free diet (iVYLISA GIP stool test and urine gluten test)

In celiac disease, identification of gluten contamination is essential for the management of the disease and for the successful conduct of clinical trials. Contaminating gluten is a confounding factor in the evaluation of a potential therapeutic effect of any experimental

celiac-related medication, since histologic, serologic and clinical endpoints are heavily influenced by the presence of gluten in the diet.

In addition to measuring symptoms through patient reported diaries, Celimmune plans to use the iVYLISA GIP-S stool and urine gluten tests, gluten assays developed to detect inadvertent gluten consumption by measuring gluten immunogenic peptides (GIP) in faeces (Comino *et al*, 2012) and urine (Moreno *et al*, 2015).

The stool test detects gluten for up to seven days after consumption, and the urine test for 1-2 days. Testing will be done every two weeks – subjects should provide a urine and optional stool sample collected up to three days before or after the visit to the sites, in order to have a good probability of identifying dietary transgressors to enable correct data interpretation. Testing will be done at a central lab. For the purpose of the study, the stool test is considered negative when the average amount of gluten of a stool sample is <300 ng GIP/g stool sample.

iVYLISA GIP stool test and urine gluten test results (positive/negative) will be presented by visit and treatment group as well as listed.

PP analysis sets will be used.

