CELIM-NRCD-001 is designed to be a Phase 2a randomized, double-blind, placebo-controlled, parallel-group study to evaluate the efficacy and safety of AMG 714 for the attenuation of the effects of gluten exposure in adult patients with celiac disease during a gluten challenge.

After signing consent subjects will be screened for the study. All subjects who meet the study entry criteria will be randomized at a 1:1:1 ratio to receive 150 mg or 300 mg AMG 714 or placebo once every two weeks for 10 weeks. Randomization will be stratified by site and sex. The study drug (AMG 714 or placebo) will be administered at the clinical site in a double-blind fashion via subcutaneous (SC) injection. Subjects will remain confined to the study site for a minimum of 1 hour after each administration of study medication. During this time the Investigator and study site staff will assess the subject for AEs and collect the required PK samples and post dose vital signs as outlined in the study schedule of events in [Appendix 1](#).

In addition to receiving study medication (AMG 714 or placebo), all subjects will be required to consume either placebo gluten or active gluten administered in a single-blind fashion. Beginning on the day following Visit 1 (i.e. Week 0/Day 1, since Visit 1 is defined as Week 0/Day 0) through Visit 2 (Week 2/Day 14), all randomized subjects will consume placebo gluten, in the form of gluten-free foodstuffs (e.g. rusks) provided by the Sponsor, twice a day (BID) at the time of two regularly consumed gluten-free meals (chosen by the subject). Starting at Visit 2, subjects will switch to consume a daily total of approximately 2-4g of active gluten, provided in the form of foodstuff identical in appearance to that provided during the two-week single-blind placebo-gluten period. These gluten-containing foodstuffs, supplied by the sponsor, will be consumed in approximately 1-2g doses BID at the time of two regularly consumed gluten-free meals (as chosen by the subject) from Visit 2 (Week 2/Day 14) through the end of the treatment period at Visit 7 (Week 12/Day 84). Consumption of additional products containing gluten will be prohibited and subjects will be expected to continue total adherence to their former GFD from the time of screening until the follow-up study visit (Visit 8, Week 16/Day 112).

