The threshold of VH:CD to receive gluten challenge was initially 2 (protocol version 1) and subsequently 1.8 (protocol version 2) before the final threshold of 1.5 VH:CD was adopted in protocol version 3. The population of subjects who received gluten challenge and had pre/post biopsies, a majority of the patients, will represent the per protocol population 1 (PP1) and will be analysed for the primary and secondary endpoints separately from the subjects who did not receive gluten challenge and had pre/post biopsies, a small fraction of the subjects who will represent the per protocol population 2 (PP2). All primary and secondary endpoints will be analysed in PP1 and PP2 separately.

All subjects will complete the BSFS at the time of each bowel movement from baseline (Visit 1, Week 0/Day 0) up to the final study visit (Visit 8, Week 16/Day 112). Subjects will complete the CeD PRO daily from baseline up to the final study visit. Subjects will also complete the GSRS at screening and, thereafter, weekly from baseline through the final study visit. The BSFS, GSRS and CeD PRO will be completed using a handheld electronic diary at times specified in [Appendix 1](#).

Safety will be monitored on an ongoing basis and subjects may undergo unscheduled visits for safety reasons, if needed. Safety will be assessed throughout the study by clinical laboratory tests, physical examination, vital signs, and AE monitoring.

[Figure 1](#) represents a schematic drawing of the study periods and visits.

Figure 1 CELIM-NRCD-001 study schematic

4 Randomisation

Randomisation, i.e. the random allocation of treatments to subject numbers, will be performed according to the design of the study. A detailed description of the randomisation method, including the size(s) of randomly permuted blocks used to balance the randomisation, will be stored at the restricted area of StatFinn server, where only the randomisation expert and the unblinded statistician will have access to. Once the data base is locked and the treatment code open, the randomisation documents will be moved to the non-restricted area.

Subjects will be randomized at a 1:1:1 allocation to receive 150 mg AMG 714 or 300 mg AMG 714, or placebo once every two weeks for a total of six administrations over ten weeks. Randomization will be stratified by site and sex.

5 Statistical hypotheses

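### The exploratory daily CeD PRO model is linear in day across the scheduled gluten on and off switches, so it dilutes the arm difference during the challenge and fits one at Day 0, before any gluten

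*SAP*

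**What the plan says.** Section 7.7.4 of the SAP specifies two models for the exploratory CeD PRO. One is "one for daily level data with time (days from baseline) as continuous variable"; the other uses weekly mean scores with week as a class variable and treatment contrasts by week. The daily program reads "model cedpro_d = cedpro_d_bl trt site sex day trt*day / solution", with day absent from the CLASS statement, and starts from "random _residual_ / subject=subjid type=AR(1"). Its coded comparisons are contrasts on `trt` alone, plus least-squares means by arm. A note adds: "Note that the proper functional form of the time (day) will be explored, e.g. square of day might be added".

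Section 3 fixes the exposure. "Subjects will complete the CeD PRO daily from baseline up to the final study visit", which is Day 112. Subjects eat placebo gluten first, and then: "Starting at Visit 2, subjects will switch to consume a daily total of approximately 2-4g of active gluten". The active foodstuffs are eaten "from Visit 2 (Week 2/Day 14) through the end of the treatment period at Visit 7 (Week 12/Day 84"). After that only the gluten-free diet remains, "until the follow-up study visit (Visit 8, Week 16/Day 112").

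**The concern.** Section 7.7.4 lets each arm follow one straight line over 113 days, so the difference between arms is also one straight line. The design imposes an off-on-off exposure whose switch days are known in advance, and no term in the model marks them. A benefit that exists only while gluten is eaten has to be spread over the whole follow-up. At stake is whether the daily model's treatment estimate describes the period in which gluten-induced symptoms can be attenuated, and whether its treatment-by-day slope can be read as a drug effect.

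**Working it through.** The SAP states no figure for CeD PRO, so there is none to reproduce. Its power figures concern VH:CD and do not bear on this point.

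**Inputs.** From the SAP: Days 0-112 (113 days, mean 56) and active gluten on Days 14-84 (71 days, mean 49). Assumptions: placebo symptoms rise by up to D on gluten, the drug prevents this fully, and diaries are complete. The SAP gives no symptom course, so several are tried. The difference is placebo minus drug, so a positive value favours the drug.

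**Step course, least squares** (excess D on Days 14-84, otherwise 0):
- Sum of squares of day = 113 × (113² − 1)/12 = 120,232.
- Cross-product = 71 × (49 − 56) × D = −497D.
- Slope = −497D/120,232 = −0.00413D per day, or −0.46D over 112 days.
- Mean = 71D/113 = 0.628D.
- Day 0: 0.628D + 56 × 0.00413D = 0.86D (truth 0).
- Day 49: 0.628D + 7 × 0.00413D = 0.66D (truth D). A line averaged over Days 14-84 equals its value at Day 49, so this is also the fitted mean during the challenge.
- Day 112: 0.628D − 56 × 0.00413D = 0.40D (truth 0).

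**Seven courses, same method** (ratio = fitted mean over Days 14-84 divided by the true mean; values in units of D):

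| Placebo course | Slope per day | Fitted Day 0 | Fitted mean | True mean | Ratio | Ratio, AR(1) 0.95 |
|---|---|---|---|---|---|---|
| Step, Days 14-84 | −0.00413 | 0.86 | 0.66 | 1.00 | 66% | 48% |
| 14-day linear rise and 14-day fall | 0 | 0.62 | 0.62 | 0.89 | 69% | 52% |
| Linear rise to Day 84, 14-day fall | +0.00326 | 0.19 | 0.35 | 0.50 | 70% | 54% |
| Linear rise to Day 84, then off | +0.00148 | 0.23 | 0.30 | 0.50 | 61% | 46% |
| Exponential, 14-day time constant both ways | +0.00301 | 0.44 | 0.58 | 0.80 | 73% | 57% |
| Step persisting to Day 98 | 0 | 0.75 | 0.75 | 1.00 | 75% | 56% |
| Step, no recovery by Day 112 | +0.00576 | 0.55 | 0.84 | 1.00 | 84% | 73% |

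The first three rows are the main courses. The SAP gives no AR(1) correlation. With assumed values of 0.5, 0.8 and 0.95 the step slope is −0.0039, −0.0034 and −0.0018D per day.

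**Where the coded contrast sits.** With `trt*day` in the model and day uncentred, the contrast on `trt` alone is the fitted difference at Day 0. In the step course that is 0.86D, on a day when no active gluten has been eaten.

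**Effect of adding a square of day.** As a main effect only, the square is common to all arms and cancels. The arm difference stays (treatment difference) + (slope difference) × day, with the misfit above. With a treatment interaction as well, the step-course fit is 0.00D at Day 0, 1.07D at Day 56 and 0.63D at Day 84 (truth D on the last two). The variation of the true difference curve that is explained rises from 8% to 74%.

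**The case against.** The case against has real weight.

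- The weekly model imposes no shape on time and gives contrasts week by week, so it can show the on/off course. Section 7.7.4 also plots individual and mean daily scores by arm. This stands, and it confines the harm to the daily model.
- The straight line is only a starting form. The note in section 7.7.4 promises to explore the form of day, and section 7.6.1 allows code changes without a SAP amendment. Data-driven shaping is ordinary for an exploratory endpoint. This stands in part. The note gives no selection rule and does not say that a square would interact with treatment; without that, the arm difference remains a line. Nor is there a need to search the data for switch days that the design already fixes.
- A reader might infer that the analysis would show an effective drug as harmful, because the slope can run the wrong way. The SAP does not support that. No slope contrast is coded, although the slope would appear among the tabulated parameter estimates. In every course in the table the fitted level difference favours the drug throughout Days 0-112. The slope's sign also depends on an assumed course: it is adverse for the abrupt step, zero for two courses, and in the expected direction for the other four.

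**Conclusion.** The point holds for the daily CeD PRO model only. Under full prevention, the fitted difference during the challenge is about two thirds of the true one by least squares, and about half in most courses under AR(1) with correlation 0.95. A difference is fitted at Day 0, where the truth is zero. Both results hold in all seven courses; only their size varies. The slope cannot be read as attenuation, since its sign follows the speed of symptom onset and offset.

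These figures rest on assumed symptom courses, an assumed correlation, complete diaries and full prevention. It would go too far to conclude that the SAP cannot assess symptom attenuation: the weekly model can, and CeD PRO is exploratory. This is a worthwhile improvement to a secondary piece of the plan and does not threaten the trial's main conclusions.

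**What to change.** In PP1, replace `day` and `trt*day` in the daily model by one of two prespecified forms:
- a gluten-phase factor (scheduled Days 0-13, 14-84, 85-112) with its treatment interaction; or
- piecewise-linear day with knots at Days 14 and 84, with all segments interacting with treatment. This suits gradual onset and offset better.

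Report each dose-versus-placebo contrast averaged over the active-gluten phase in place of the contrast at Day 0.

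Define phase by scheduled days, not by each subject's actual gluten dates. Stopping gluten early happens after randomisation and may be related to symptoms, so phases set by actual dates could bias the contrast. PP2, defined in section 7.1 as no challenge or less than a week of it, has little or no active-gluten phase and needs no such contrast.

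Cost: a few lines of SAP text and code, and no new data. The phase factor has three means per arm in place of an intercept and a slope (one extra parameter). The piecewise line has an intercept and three slopes (two extra).

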7.2.1 Definition of derived variables

Geometric mean will be calculated as:

$$\text{mean}_{\text{geo}} = \sqrt[n]{x_1 x_2 \cdots x_n} = \exp\left\{\frac{1}{n} \sum_{i=1}^n \ln x_i\right\}.$$

Values that are missing or not available will be ignored in calculation of geometric mean.

CV%_{geo} will be calculated using the following formula:

$$\text{CV\%}_{\text{geo}} = 100\% \cdot \sqrt{\exp V_{\ln} - 1}.$$

Values that are missing or not available will be ignored in calculation of CV%_{geo}.

Absolute change from baseline for a given treatment needs to be calculated, the following formula will be used:

$$\text{Absolute change from baseline} = \text{Post-baseline value} - \text{Pre-dose value}.$$

For weekly scores, Week 0 score is considered to be the baseline value. If Week 0 score is not available, the first non-missing result within 2 weeks of treatment will be used as baseline. For daily scores (e.g. CeD PRO), Day 0 score is considered to be the baseline, in case Day 0 score is not available, the first non-missing result within 2 weeks of treatment will be used as baseline. Otherwise, the given subject will be considered non-evaluable for the specific test. In case pre-dose value doesn't exist (i.e. for biopsy endpoints), screening value will be used as baseline.

In the case where relative (%) change from baseline needs to be calculated, the following formula will be used:

$$\text{Relative (\%)} \text{ change from baseline} = (\text{Post-baseline value} - \text{Pre-dose value}) / (\text{Pre-dose value}) \cdot 100\%.$$

For weekly scores, Week 0 score is considered to be the baseline value. If Week 0 score is not available, the first non-missing result within 2 weeks of treatment will be used as baseline. For daily scores (e.g. CeD PRO), Day 0 score is considered to be the baseline, in case Day 0 score is not available, the first non-missing result within 2 weeks of treatment will be used as baseline. Otherwise, the given subject will be considered non-evaluable for the specific test. In case pre-dose value doesn't exist (i.e. for biopsy endpoints), screening value will be used as baseline.

Body mass index (BMI) is calculated using the formula:

$$\text{BMI (kg/m}^2\text{)} = \text{weight (kg)} / [\text{height (m)} * \text{height (m)}].$$

Body surface area (BSA) is calculated using Dubois' formula:

$$\text{BSA (m}^2\text{)} = 0.007184 * \text{height (cm)}^{0.725} * \text{weight (kg)}^{0.425}.$$

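### The daily CeD PRO model's only treatment contrast is the fitted arm difference at Day 0, before active gluten starts

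*SAP*

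**What the plan says.** Section 7.7.4 of the SAP plans two models for the CeD PRO total, "one for daily level data with time (days from baseline) as continuous variable" and one by week with week categorical. In the daily program day is absent from the CLASS statement, and the fixed part is "model cedpro_d = cedpro_d_bl trt site sex day trt*day / solution".

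The 150 mg contrast is "estimate '150 mg AMG 714 vs Placebo' trt 1 0 -1 /alpha=0.05 cl". The 300 mg contrast has the same form. Arm means are requested by "lsmeans trt /alpha=0.05 cl", with no day named and no difference requested. On the shape of time the section adds: "Note that the proper functional form of the time (day) will be explored, e.g. square of day might be added".

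The reporting sentence covers both models: "The modelling results (parameter estimates, covariance parameter estimates, estimated treatment effect, marginal means estimates and results of the check of assumptions".

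Two other places fix the calendar. Section 7.2.1: "For daily scores (e.g. CeD PRO), Day 0 score is considered to be the baseline". Section 3: "Starting at Visit 2, subjects will switch to consume a daily total of approximately 2-4g of active gluten"; Visit 2 is Day 14, and the challenge runs to Visit 7, Day 84.

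**The concern.** With an arm-by-day slope in the model, the treatment difference changes with the day, so a single treatment effect has no meaning until a day is named. The SAP names none, and the code defaults to Day 0. The trial asks whether AMG 714 attenuates the response to gluten, and at Day 0 nobody has yet taken active gluten in the study.

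The report could therefore carry a row with a 95% confidence interval that looks like the daily treatment effect but describes the start of the fitted lines. It could disagree with the arm means printed beside it and with the weekly results.

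**Working it through.** **Inputs.** Day 0 to 112, uncentred and continuous (Section 7.7.4). Day 0 is baseline (Section 7.2.1). Active gluten runs from Day 14 to Day 84 (Section 3). CeD PRO total: nine items scored 0 to 10, so 0 to 90, lower being milder (Section 7.7.4). The SAP states no expected effect or time course, so the shapes below and the maximum benefit of -10 are assumptions.

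**1. What the contrast estimates.** Let arm j have intercept a_j and slope l_j. The fitted difference from placebo at day d is

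(a_j - a_P) + (l_j - l_P) × d.

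Coefficients on trt alone give a_j - a_P, the value at d = 0. The software does not fill in trt*day coefficients, because that term contains a continuous variable that trt does not. In a simulated data set fitted by least squares, the trt coefficient was 1.49 and the predicted difference at Day 0 was also 1.49. The same fit gave 0.08 at Day 14, -4.16 at Day 56 and -6.98 at Day 84.

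**2. What the means estimate.** Without a stated day, the arm means are taken at the average day, (0 + 112)/2 = 56 with complete diaries. Means and contrast agree only if the fitted slopes are equal.

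**3. Effect of a day-squared term.** The square is also zero at Day 0. With the contrast unchanged, the row still refers to Day 0.

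**4. Size.** Each assumed difference curve over Days 0 to 112 was projected by generalised least squares on a straight line under 12 covariance matrices: independence (compound symmetry gives the same estimates); AR(1) with correlation 0.3, 0.5, 0.8, 0.9 and 0.95; and a random intercept share of 0.2, 0.4 or 0.6 combined with AR(1) at 0.3 or 0.5.

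Under independence two cases can be done by hand, with Σ(d - 56)² = 120,232:

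- Benefit of -10 from Day 15, held to Day 112: mean = -10 × 98/113 = -8.673; slope = -7,350/120,232 = -0.0611; Day 0 value = -8.673 + 56 × 0.0611 = -5.2.
- Benefit growing linearly from 0 at Day 14 to -10 at Day 84, then held: mean = -5.619; slope = -13,675/120,232 = -0.1137; Day 0 value = -5.619 + 56 × 0.1137 = +0.75.

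Ranges over the 12 matrices:

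| Assumed shape | True mean, Days 15-84 | Planned row (Day 0) | Same line at Day 56 |
|---|---|---|---|
| Constant from Day 0 | -10 | -10 | -10 |
| Starts with challenge, held | -10 | -3.4 to -5.2 | -7.7 to -8.7 |
| Grows Days 14-84, then held | -5.1 | +0.1 to +0.75 | -5.5 to -5.6 |
| Full at Day 0, fading to zero at Day 112 | -5.6 | -10 | -5.0 |
| Only during challenge | -10 | -5.5 to -8.3 | -4.6 to -6.2 |

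**5. Reading the line at Day 49, (14 + 84)/2.** Under independence the held benefit gives -8.673 + 7 × 0.0611 = -8.2, and the growing benefit gives -5.619 + 7 × 0.1137 = -4.8. For a benefit confined to the challenge, the straight line at Day 49 gives -4.8 to -6.5, further from -10 than the planned row in all 12 matrices. Adding the square and its treatment interaction gives -9.8 to -10.7 for that shape. The standard error is then 1.01 to 1.45 times that of the straight-line Day 49 contrast.

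**The case against.** CeD PRO is exploratory and no primary or secondary conclusion uses it. The weekly model is meant to supply week-specific contrasts across the challenge. Daily slopes and mean curves are also reported. Section 7.6.1 lets code be modified without an amendment, and Section 7.7.4 leaves the form of time open. All of this limits the weight and makes correction cheap. It does not cure the fault, because no text names another day, and a day chosen after unblinding would depend on the data.

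It is also fair to say that the reporting sentence is generic and that the table templates in Appendix 4 are not shown. A reader might infer that the final table certainly prints the Day 0 gap as the treatment effect. The SAP supports only that it is the sole arm contrast the daily program requests, and so the evident source.

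A reader might further infer that a quadratic with treatment interaction is required. The documents give no time course to support that, and the advantage depends on the shape. For a benefit on Days 15 to 35 only (true mean -3.0), the quadratic Day 49 contrast gives -2.4 to -2.6 and the planned row -2.7 to -4.9, so the planned row is closer under some matrices.

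The weekly contrasts cannot be fully checked as printed: some interaction rows list 18 coefficients per arm for 17 weeks. This may come from text conversion, and no fault is claimed there.

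**Conclusion.** The point stands as a mis-specified contrast in an exploratory analysis. That the row refers to Day 0 follows from the model and code and needs no assumption. How far it lies from the difference during the challenge rests on the assumed shapes, the -10 maximum and complete diaries. Of the five shapes tabulated, only the constant effect from Day 0 is recovered.

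A reader might infer that the row always understates benefit. It does not: an early benefit that fades is overstated (-10 against -5.6). Nor would a Day 49 reading be the average challenge-period effect. For a benefit that grows to Day 84 and fades by Day 112, even the quadratic Day 49 value is -6.1 to -6.3 against a mean of -5.1. It is a fitted difference at one day. The challenge argument applies to PP1 only, since PP2 received no challenge or less than a week of it. Nothing here touches the primary or secondary analyses.

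**What to change.** Before unblinding, state one day within the challenge for the daily contrast. With Day 49 as the example:

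- 150 mg: `trt 1 0 -1 trt*day 49 0 -49`
- 300 mg: `trt 0 1 -1 trt*day 0 49 -49`
- Means: `lsmeans trt / at day=49 diff cl`

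Label the row *fitted difference at Day 49*, and say that it is read as a difference during the challenge in PP1 only.

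If the planned exploration adds day*day, also include trt*day*day, with coefficients 2401 0 -2401 and 0 2401 -2401 (49² = 2,401), and hold day*day at the same day in the means. The quadratic is advisable, because a straight line at Day 49 can miss a benefit confined to the challenge, but it is optional.

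The cost is a few lines of code and one sentence, with no new data. With three arms the quadratic adds three parameters (one common square, two treatment differences in it) and widens intervals by 1 to 45% against a straight-line Day 49 contrast.
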